2.15.6 Analysis of Safety Variables

Safety will be assessed through the degree of pain/discomfort related to the procedure (universal pain scale) and the collection of Adverse Events throughout the course of the study. For each treatment group these variables will be summarized. The summaries will include the number and percent of patients for each outcome. No statistical comparisons will be performed for any of these variables.

2.16 Randomization

One flank will receive treatment with the TempSure® Firm handpiece and the other will not receive treatment to serve as a control. Randomization will occur using a validated method determined by the Investigator, such as flipping a coin or an electronic system such as Virtual Coin Toss (www.virtualcointoss.com).

3.0 RISK ANALYSIS AND MANAGEMENT

3.1 Risk Determination

This device study used in this study does or does not meet the FDA definition for a Significant Risk Device study per 21 CFR 812.3(m). Therefore, the sponsor determines that this is a non-significant risk device study.

Significant risk device means an investigational device that:

- (1) Is intended as an implant and presents a potential for serious risk to the health, safety, or welfare of a subject;
- (2) Is purported or represented to be for a use in supporting or sustaining human life and presents a potential for serious risk to the health, safety, or welfare of a subject;
- (3) Is for a use of substantial importance in diagnosing, curing, mitigating, or treating disease, or otherwise preventing impairment of human health and presents a potential for serious risk to the health, safety, or welfare of a subject; or
- (4) Otherwise presents a potential for serious risk to the health, safety, or welfare of a subject.

3.2 Risk Management

The Investigator in this clinical trial has been invited to participate based on his/her previous experience with the use of the system and/or similar systems and industry experience. Experience with treatments is the most critical element in managing subject risk in this trial.

In addition, as with any study, there is a risk of bias. To minimize/avoid bias subjects will be randomized and blinding will occur as determined by the study design. Objective evaluation methods may also be used in conjunction with subjective evaluation methods when feasible. The value of the compensation to the clinical investigator for conducting the study is not influenced by the study outcome. If photographic results are listed as the primary objective, they are to be evaluated by blinded evaluators who did not partake in the study. If information concerning investigator assessment of improvement or investigator satisfaction is collected, then it is not listed as an objective for the study.

All other known risks will be disclosed to the subject via the informed consent process. Since this is an elective procedure and the subjects are volunteers, it can be assumed that their signature on the informed consent is indicative of their agreement to accept the risks involved.

The risks to the subjects who participate in this study are the same as those for the subject undergoing similar noninvasive lipolysis treatment(s). It is possible to have an adverse reaction to the TempSure device use. There may be some side effects that we do not know about yet.

3.3 Risk Analysis

CONTEXT OF THE PROPOSED INVESTIGATION:

Radiofrequency (RF) technology is commonly used in surgery, non-invasive treatments and aesthetic applications. RF technology is a safe method for non-ablative (A non-wounding device treatment which heats underlying skin) treatment because energy can be precisely delivered through the skin to the subcutaneous adipose tissue beneath without damaging the epidermis.^{vi}

According to published data, the elevation of tissue temperature between 42°C to 47°C can affect the cellular matrix of the adipose tissue creating injury to the adipocytes and prompt an inflammatory response.^{vii} Gradually, the treated adipocytes will be removed by the human body through the inflammatory clearing process which takes weeks to months. The regeneration of adipose tissue is very slow (over years) and the total volume of the fat in treatment area will decrease due to the loss of adipocytes.

ASSESSMENT OF RISKS OF THE PROPOSED INVESTIGATION:

There are two risks identified with the TempSure device used in this study. The first risk identified is the lack of clinical data for evidence of effectiveness of Envi handpieces for the treatment of lipolysis. Parameters need to be further investigated to be optimized for efficacious results. The second risk identified is the safety of treatment with the TempSure® Firm handpieces. Since the TempSure® Firm handpieces have not been cleared for use for lipolysis and has limited safety data for this indication, optimizing the safety profile is necessary.

The risk identified with the overall clinical investigation is the integrity of the data collected.

There are multiple clinical mitigation strategies for the risks identified. Proper training on the device and protocol will be performed. Data from prior investigations will be utilized to minimize side effects and optimize treatment outcomes. Monitoring of the study will be implemented to minimize subject and data risks.

ASSESSMENT OF BENEFITS OF THE PROPOSED INVESTIGATION:

The subject may or may not have a reduction in unwanted fat.

CONSIDERATION OF PATIENT PREFERENCE INFORMATION:

Many physicians support the use of radiofrequency devices for non-invasive cosmetic treatments due to current patient satisfaction of cosmetic results with the currently available devices. However, there is still a level of interest in novel technologies that could reduce the need for invasive treatments for fat reduction.

ASSESSMENT OF UNCERTAINTY:

There is uncertainty of the efficacy of the treatment when TempSure® Firm is used for the treatment of unwanted fat.

CONCLUSION:

The TempSure® Firm handpieces used in this study have not been FDA cleared for use for the treatment of wanted fat (lipolysis) but pose no more risk than the currently cleared indications for use.

A previous safety study, CYN18-RF-TISSUE-RD, was conducted using excised human abdominoplasty tissue to test various radiofrequency parameters with the 60mm handpiece. Another safety study, CYN19-TS-ABDOM, was conducted using patients scheduled for an abdominoplasty surgery to use in-vivo tissue to test various radiofrequency parameters with the 60mm handpiece. Thermal measurements of treatment zones were collected to evaluate the depth of penetration and effects on human tissue.

Studies CYN17-RF-CLINIC and CYN19-TS-ENVI-ABD collected safety and efficacy data using the 25mm, 30mm, and 60mm handpieces on various body areas, including the abdomen.

Patient population to be enrolled in this clinical study:

Total anticipated population: 68 Subjects

Age Range years old: 18 – 55 years old

Gender: Male or Female

Condition: Unwanted fat on flanks

4.0 DEVICE DESCRIPTION AND SPECIFICATIONS

The TempSure® device used in this study is currently cleared by the U.S. Food and Drug Administration (the FDA). The TempSure® device received 510(k) clearance under K171262 on September 22, 2017 for:

- The 10mm, 15mm, and 20mm TempSure Envi handpieces are indicated for non-ablative treatment of mild to moderate facial wrinkles and rhytids.
- The 18mm, 25mm, and 30mm TempSure Envi handpieces provide heating for the purpose of elevating tissue temperature for selected medical conditions such as temporary relief of pain, muscle spasms, and increase in local circulation.
- The Massage device is intended to provide a temporary reduction in the appearance of cellulite.
- Coagulation/Hemostasis: Using the surgical handpieces and accessories, general surgical procedures including urologic, thoracic, plastic, reconstructive, and gynecological procedures where electrosurgical coagulation of tissue is performed.

And received 510(k) clearance under K182365 on October 24, 2018 for:

- Cutting: snoring, submucosal palatal shrinkage, traditional uvulopalatoplasty (RAUP), myringotomy with effective hemorrhage control, epistaxis treatment, turbinate shrinkage, skin incisions, biopsy, cysts, abscesses, tumors, cosmetic repairs, development of skin flaps, skin tags and blepharoplasty.

- Blended Cutting and Coagulation: snoring, submucosal palatal shrinkage, traditional uvulopalatoplasty (RAUP), myringotomy with effective hemorrhage control, epistaxis treatment, turbinate shrinkage, skin tags, papilloma keloids, keratosis, verrucae, basal cell carcinoma, nevi, fistulas, epithelidma, cosmetic repairs, cysts, abscesses, and development of skin flaps.
- Fulguration: basal cell carcinoma, papilloma, cyst destruction, tumors, verrucae, hemostasis.
- Bipolar: pinpoint precise coagulation, pinpoint hemostasis in any field (wet or dry). Snoring, submucosal palatal, shrinkage, traditional uvulopalatoplasty (RAUP), myringotomy with effective hemorrhage control, epistaxis treatment and turbinate shrinkage

The 60mm handpiece of the TempSure® device received 510(k) clearance under K190678 on July 24, 2019 to provide heating for the purpose of elevating tissue temperature for selected medical conditions such as temporary relief of pain, muscle spasms, and increase in local circulation.

The TempSure® device is considered investigational because TempSure® Firm handpieces used in this study are not cleared for use for lipolysis.

Changes to the TempSure® device are not anticipated during the investigation.

The TempSure® Device Specifications are:

Surgical Connector	1 surgical monopolar port
Neutral Connector	One universal neutral connector compatible with Cynosure neutral electrodes
Smart Handpiece Connectors	One 4-pin circular connector for both RF energy delivery and temperature sensing (monopolar)
Modes of Operation	Select the Smart Handpiece or Surgical mode of operation
Maximum Power	
Temperature-Sensing Handpieces
 
⚠ 10mm, 15mm, and 20mm handpieces have a maximum GUI setting of 70, which provides output power of 120 Watts (+/- 20%).
 
⚠ 18mm handpiece has a maximum GUI setting of 25, which provides output power of 25 Watts (+/-20%).
 
⚠ 25mm and 30mm handpieces have a maximum GUI setting of 80, which provides output power of 165Watts (+/- 20%).
 
⚠ 60mm handpieces have a maximum GUI setting of 100, which provides output power of 300 Watts (+/- 20%).
 
⚠ FlexSure applicators are controlled by setting the temperature. During treatment, power can reach a maximum output of 300 Watts (+/- 20%).
 
Ensuring that the neutral pad recommended for use with the 60mm handpiece and flexible applicator has sufficient current carrying capacity so as to assure that there is no unacceptable temperature rise under the pad is an essential performance of the TempSure platform.

The TempSure® device Operator Manual: Attachment I

The TempSure® consumables are: Handpieces, NEM Pads, Gel

5.0 MONITORING PROCEDURES

The Sponsor Standard Operating Procedure (SOP) for monitoring the investigative site will be followed. The sponsor will train the site following sponsor SOP's and may be present at initiation of treatment. The sponsor will also monitor the site periodically. The Investigator/Institution will permit trial-related monitoring, audits, IRB/IEC review, and regulatory inspections by providing direct access to source documents. The sponsor may request intermediate data following each visit to evaluate treatment progress. Case Report Forms will be reviewed for current data and Regulatory Binders will also be reviewed for correct documents. The sponsor will collect data at the end of the follow up period. The sponsor will list the study on clinicaltrials.gov as required by FDA regulations.

The monitoring plan for this study is outlined in the Cynosure Monitoring Plan.

ASSIGNED CLINICAL RESEARCH MONITOR:

Monitor #1

Name: [name]

Institution: Cynosure, LLC

Address: [name]

6.0 LABELING

Sample labeling will follow FDA regulations and the sponsor standard operating procedure.

If applicable the TempSure® device label will include, (in accordance with 801.1):

Statement: "CAUTION--Investigational device. Limited by Federal (or United States) law to investigational use."

Additionally, the label or other labeling will describe all relevant contraindications, hazards, adverse effects, interfering substances or devices, warnings, and precautions.

7.0 CONSENT MATERIALS

Forms and informational materials which are provided to the subject during the informed consent process are listed below:

Form/Informational Material Description
Pre and Post Treatment Instructions
Informed Consent Form
Universal Pain Assessment Tool

9.0 OTHER INSTITUTIONS

If a part of the study is conducted by an institution that has not previously been identified within the Investigational plan each institution's contact information will be documented below;

No other institutions will be part of this study.

10.0 ADDITIONAL RECORDS AND REPORTS

Additional records and reports will be maintained on the investigation in addition to those prescribed in 21 CFR 812.25 sub-part G.

Additional Records and Reports:

Report	Submit To	Description/Constraints
N/A	N/A	This is a non-IDE study; no additional records or reports will be maintained.

11.0 PREGNANCY

Females may not participate in this study if they are pregnant, breastfeeding, were pregnant within the last three months or are planning a pregnancy during the study.

If the subject thinks they have become pregnant during the study, they must inform the Investigator immediately. If she becomes pregnant or thinks that she may be pregnant, she will be removed from the study and will be asked to perform a final evaluation similar to that of the final follow-up visit. The Investigator may request to track the pregnancy and will report the pregnancy to the Sponsor.

12.0 SUBJECT WITHDRAWAL

The subject is free to withdraw from this study at any time. The subject must inform the Investigator immediately if they intend to withdraw. To terminate the subject's participation in this study, they must contact the Investigator at the contact information listed on page one of the informed consent form. They will be asked to come to the study clinic or Investigators office to complete a final follow up visit and may be asked to perform end of study procedures. Their decision to participate in this study or to withdraw from this study will not influence the availability of their future medical care and will involve no penalty or loss of benefits to which they are otherwise entitled.

The Investigator in charge of the study can remove the subject from this study without their consent for any reason, including, but not limited to:

- His/her judgment that any condition or circumstance may jeopardize their welfare or the integrity of the study.
- Their failure to follow the instructions of the Investigator(s).
- If the study is stopped by the sponsor and/or Investigators participating in the study prior to completion.

Data collected prior to withdrawal will be used in data analysis but after withdrawal no further data will be collected.

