2.15.3 Patient Populations

Interim results may be collected and reported. All data will be analyzed at the end of the study. The primary analysis will be performed by the intention-to-treat approach. Everyone who begins the treatment is part of the study whether he or she completes the study or not. Additional per-protocol analysis may also be performed on subjects who complete the entire clinical trial according to the protocol. The most appropriate method of handling missing values will be chosen based on the trial's goals, endpoints and context.

The analysis of demographic, medical history, and efficacy variables will be based on all patients who are randomized and receive at least one treatment. The analysis of safety data will be based on all patients who are randomized, receive at least one treatment, and have at least some safety data.

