14.0 ADVERSE REACTIONS DEFINITIONS AND REPORTING REQUIREMENTS

All adverse events that occur, starting from the time of the first treatment, will be recorded in the source documents and Case Report Forms (CRF).

Adverse Events (AE) occurring will be captured and followed until the condition resolves, stabilizes, is otherwise explained, or the subject is lost to follow-up. Subjects will be instructed that they may contact the Investigator at any time throughout the course of the study.

The Investigator and/or designated study staff will review each event and assess its relationship to the study device (not related, unlikely, possible, probable, and highly probable). The following definitions will be used for rating relationship to the TempSure® Firm treatments:

- Not related – The event is clearly related to other factors such as the subject's clinical state, therapeutic interventions, or concomitant medications administered to the subject.
- Unlikely – The event was most likely produced by other factors such as the subject's clinical state, therapeutic interventions, or a concomitant medication administered to the subject; and does not follow a known response pattern to the investigational product.
- Possible – The event follows a reasonable temporal sequence from the time of investigational product administration; **and/or** follows a known response pattern to the study sampling sessions; **but** could have been produced by other factors such as the subject's clinical state, therapeutic interventions, or concomitant medications administered to the subject.
- Probable – The event follows a reasonable temporal sequence from the time of investigational product administration; **and** follows a known response pattern to the investigational product; **and** cannot be reasonably explained by other factors such as the subject's clinical state, therapeutic interventions, or concomitant medications administered to the subject.

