Adverse events, whether serious or non-serious, will be followed until the condition is resolved, stabilized, otherwise explained or the subject is lost to follow-up. Adverse events will be captured throughout the study and where appropriate, medical tests and examinations will be performed to document the resolution of event(s). Outcomes may be classified as resolved, improved, unchanged, worse, fatal, unknown or lost to follow-up. Following the resolution of any study-associated adverse events there will be no further adverse event reports for that subject.

Reporting Adverse Events:

Report	Submit To	Description/Constraints
Adverse Events, Unanticipated Adverse Device Effect	IRB and Sponsor	If an unforeseen complication is determined to be an unanticipated adverse device effect, the investigator's report must be submitted within 10 working days after the investigator first learns of the effect.
Serious Adverse Events	IRB and Sponsor	The sponsor must be notified within 24 hours of serious adverse events. The IRB must be notified within 10 working days of serious adverse events as defined by FDA guidelines.

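### The bar on data after withdrawal is not limited to withdrawn consent: it conflicts with adverse event and pregnancy follow-up and leaves week-12 outcomes missing for subjects kept in the primary analysis

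*Combined protocol and SAP*

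**What the plan says.** Section 12.0 (Subject Withdrawal) closes with the rule: "Data collected prior to withdrawal will be used in data analysis but after withdrawal no further data will be collected". Earlier in the same section, the plan says of withdrawing subjects: "They will be asked to come to the study clinic or Investigators office to complete a final follow up visit". The section also lets the Investigator remove a subject without that subject's consent for any reason. The listed examples are risk to welfare or study integrity, not following instructions, and the study being stopped.

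Three other places bear on this:

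- Section 14.0 on adverse events: "Adverse Events (AE) occurring will be captured and followed until the condition resolves, stabilizes, is otherwise explained, or the subject is lost to follow-up". It says so again later: "Adverse events, whether serious or non-serious, will be followed until the condition is resolved, stabilized, otherwise explained or the subject is lost to follow-up".
- Section 11.0 on a subject who becomes pregnant: "she will be removed from the study and will be asked to perform a final evaluation similar to that of the final follow-up visit". It then allows the Investigator to ask to track the pregnancy and requires a report to the sponsor.
- Section 2.15.3 makes intention-to-treat primary: "Everyone who begins the treatment is part of the study whether he or she completes the study or not". It leaves the missing-data method to be chosen later.

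The photograph, caliper and satisfaction assessments that count are those 12 weeks after the last treatment (Sections 2.15.2 and 2.15.5). Section 2.11 allows replacement, with approval, of subjects who withdrew or were withdrawn.

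**The concern.** Ending data collection is right when a subject withdraws consent to it. As written, the rule goes further. Nothing separates leaving the study from refusing follow-up, and a subject removed for not following instructions has refused nothing.

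Two things are at stake. The first is the safety record. A site with an adverse event still open at withdrawal, or a pregnancy in a removed subject, has two instructions that cannot both be followed. The plan lists burns, scarring and nodules as possible effects (Section 2.14), describes safety data for this indication as limited (Section 3.3), and makes the side effect profile a success criterion (Section 2.15.1).

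The second is the efficacy verdict. Week-12 outcomes go uncollected for subjects who count in the primary analysis, with no rule for filling the gap. Photographs and satisfaction are both judged against a fixed 80%. The study is open-label (Section 2.2), so leaving or being removed may depend on visible response. Replacing such subjects does not recover their outcomes.

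**Working it through.** **1. The passages side by side**

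| Situation | Section 12.0 rule | Other text | Can both be followed? |
|---|---|---|---|
| Adverse event open at withdrawal | No further data | Section 14.0: follow to resolution, stabilisation, explanation or loss to follow-up | No. Withdrawal is not a listed end, and a subject who can be reached is not lost |
| Pregnancy after removal | No further data | Section 11.0: tracking allowed | No. Tracking happens after removal |
| Final visit of a withdrawing subject | No further data | Section 12.0: visit requested | Yes, if the visit is the last step before withdrawal takes effect |
| Week-12 outcome of a treated leaver | No further data | Section 2.15.3: subject is in the primary analysis | Yes formally, but the outcome is missing |
| Stops treatment early, stays in study | Does not apply | Sections 2.9 and 2.12: visits run from the last treatment | Yes. The week-12 visit is kept |

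Does the rule reach subjects removed by the Investigator? It speaks only of withdrawal. Section 2.11 uses that word for subjects who were withdrawn as well as those who withdrew, so the natural reading is yes, though the text does not settle it.

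**2. The plan's sample size**

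Inputs from Section 2.15.2: 80% vs 50% (difference 0.30), SDs 0.20 and 0.50, two-sided 0.05, power 95%.

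- Normal approximation, per group: (0.50² + 0.20²)(1.960 + 1.645)² / 0.30² = 0.29 × 12.995 / 0.09 = 41.9. The t-based calculation with pooled degrees of freedom gives 95.06% power at 43. The stated 43 is reproduced, as the size of one group against a hypothetical control.
- Calipers: difference 7.0 − 0.7 = 6.3 mm, SD 5.8, paired t-test. Power is 94.8% at 13 and 96.3% at 14. The stated 14 is reproduced.
- Spare enrolment: 68 − 43 = 25, and 25/68 = 36.8%.
- Power on the plan's own inputs (unequal-variance t-test): 99.0% with 61 subjects and 98.1% with 54.

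Losing 10% to 20% of subjects therefore costs little power. The exposure is bias.

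**3. How far missing subjects can move the 80% verdict**

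The documents give no withdrawal rate, so the numbers missing are assumptions. Also assumed: 68 treated, and one photo pair per subject per reviewer. For m missing, let c be the smallest number correct that gives at least 80% of the 68 − m assessed. The rate over all 68 then lies between c/68 (all missing incorrect) and (c + m)/68 (all missing correct).

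| m | Observed | Lower bound | Upper bound |
|---|---|---|---|
| 3 (4%) | 52/65 = 80.0% | 52/68 = 76.5% | 55/68 = 80.9% |
| 7 (10%) | 49/61 = 80.3% | 49/68 = 72.1% | 56/68 = 82.4% |
| 14 (21%) | 44/54 = 81.5% | 44/68 = 64.7% | 58/68 = 85.3% |

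The verdict can also move the other way. With 7 missing, 48/61 = 78.7% fails, yet (48 + 7)/68 = 80.9% would pass.

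If missing counts as failure, 0.80 × 68 = 54.4, so 55 correct are needed. With 14 missing only 54 remain, and the criterion cannot be met. The same arithmetic applies to satisfaction.

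**The case against.** The best defence is that the rule is ordinary and most of the apparent conflict dissolves on a fair reading. Much of that stands.

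- A reader might infer that Section 12.0 contradicts itself by requesting a final visit. The section runs in sequence from intention to withdraw, to final visit, to end of participation, so the visit can precede withdrawal. The evaluation in Section 11.0 can be read the same way. The pregnancy tracking cannot, and a visit at withdrawal is generally not a week-12 assessment.
- A reader might infer that the rule contradicts intention-to-treat. Section 2.15.3 says who is analysed, not what must be collected, and it expects missing values. The analysis is weakened, not contradicted.
- A reader might infer that everyone who stops treatment is lost. Treatment is up to five sessions and follow-up runs from the last one, so those who stay in the study keep both visits.
- A reader might infer that an adverse event open at withdrawal would have no recorded outcome. Its status can be recorded at the final visit, and Section 14.0 allows unchanged, worse or unknown. What may be missing is the later course.
- A reader might infer that the result must be flattered, or that 37% loss is expected. The direction is unknown, since subjects also leave for pregnancy or non-compliance. The 37% is spare enrolment, which Section 2.15.2 also assigns to departures from its assumptions. Some losses would occur under any wording.

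The conflicts on adverse events and pregnancy remain, as does the avoidable loss of week-12 data from subjects who have not refused follow-up.

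**Conclusion.** The concern holds in a limited form. The rule conflicts outright with adverse event follow-up in Section 14.0 and with pregnancy tracking in Section 11.0. It also makes week-12 outcomes missing for treated subjects who withdraw or, on the natural reading, are removed, while the plan counts them in the primary analysis without a missing-data method.

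The size cannot be fixed because no dropout rate is stated. Under the assumptions above, 7 missing of 68 makes an observed 80.3% compatible with 72.1% to 82.4%. Even 3 missing spans the threshold, at 76.5% to 80.9%. These are extreme bounds for one reviewer's results, not forecasts, and they attribute every loss to this rule. They show that a fixed 80% criterion can be crossed in either direction. The planned sample size need not change.

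**What to change.** In Section 12.0, limit the no-further-data rule to subjects who withdraw consent to data collection. State that other subjects who leave or are removed are asked to attend the 6- and 12-week assessments already scheduled in Section 2.12 (photographs, calipers, questionnaire, adverse events). Make two exceptions: when the study itself is stopped, and when the Investigator judges that attending would jeopardise the subject's welfare. Say explicitly whether removal by the Investigator counts as withdrawal.

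Reconcile Sections 11.0, 12.0 and 14.0 so that they give one instruction on adverse events and pregnancies still open at withdrawal or removal.

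The cost is protocol and consent wording and a small number of retained visits. Some subjects will still decline or be unreachable, so the change reduces missing data without removing it.
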